5.2 Primary Safety Endpoint

The primary safety endpoint was defined as the occurrence of hemostatic interventions/procedures completed for post-operative bleeding related to the transection of the PA and PV during VATS lobectomy with the use of SOC or PVS. Hemostasis intervention was defined as bleeding that occurred post-operatively requiring blood or blood product transfusion or an additional surgical procedure (related to PA and PV transection). No hemostasis intervention was defined as no interventions needed for post-operative bleeding (related to PA and PV transection). This endpoint was recorded at the subject level as it was based on post-operative interventions and not specific to any individual firing.

Assuming an approximate background intervention rate of 6% in each group, the given sample size will provide reasonable precision in the estimation of the intervention rate in each treatment group to an expected margin of error for a 95% confidence interval of at most 2.9%.

9 Data Monitoring Committee (DMC)

No Data Monitoring Committee was planned or utilized during this study.

10 Analyses to be Conducted

10.1 General Conventions

Subject data will be summarized using listings and tables. All eCRF data will be listed per subject for all subjects. Descriptive statistical analyses will be provided for pre-specified study endpoints. Summaries for continuous variables will include number of observations (n), mean, standard deviation, median, minimum, and maximum. Summaries for categorical variables will include number and percentage.

Analyses will be conducted using SAS software version 9.4 or higher. During the course of analysis programming of tables that are mocked up in this SAP, minor modifications may become necessary. Examples of these minor modifications include, but are not limited to, re-wording of a footnote, addition of a footnote, re-labeling of a column, or addition or removal of a column from a listing. In cases where modifications to tables or listings are not related to a change in statistical analysis methodology or conclusions that could be made on the originally proposed methodology, then no amendment of the SAP is necessary. Amendment of the SAP is required in any case where changes to statistical analyses that were planned in the original signed SAP are proposed.

10.2 Disposition of Study Subjects

Subject disposition will be summarized by randomized treatment group and overall using counts and percentages. The number and percentage of subjects in each analysis set will be tabulated. Additionally, the number and percentage of subjects completed and discontinued will be tabulated along with the specific reasons for discontinuation.

10.3 Demographic, Baseline, and Surgical Characteristics

Summary statistics of subject demographics (age, gender, race, and ethnicity) will be presented by randomized treatment group and overall for the Full Analysis Set. Surgical characteristics including, at minimum, lobe location, calcified hilar lymph node presence, number of ports used, number of pulmonary arteries transected, number of chest tubes placed, ASA physical status, estimated blood loss, conversion to open, requirement for blood transfusion, procedure duration, and number of chest tubes will be summarized by randomized treatment group and overall. Results of tumor assessments performed by the pathology laboratory (including tumor stage, maximum tumor diameter, maximum tumor depth, primary TNM classification, presence of distant metastasis, and confirmation of non-small cell lung cancer) will also be summarized by randomized treatment group and overall.

10.4 Primary Endpoint Analyses

For the primary performance endpoint, summary statistics and 95% confidence intervals will be provided for the number and frequency of interventions for the set of SOC subjects and PVS subjects separately. This will be performed based on the total number of firings. An intervention is defined as any firing which is classified as a hemostasis intervention. To establish that the intervention rate is not increased compared to SOC, a 95% confidence interval for the difference in the proportion of firings requiring interventions for PVS minus SOC will be calculated and the powered vascular stapler will be considered to have acceptable performance if the upper bound of the 95% confidence interval does not exceed 3%.

The following SAS code will be used to generate 95% confidence intervals for the individual treatment groups as well as the difference between groups:

```
proc sort data=hemo_interv;
  by TrtGroup descending event;
run;
proc freq data=hemo_interv order=data;
  tables TrtGroup*event/binomial riskdiff;
run;
```

This code assumes that the dataset hemo_interv contains one record per firing, the variable ‘TrtGroup’ contains the identifier for randomized treatment group (the SOC group should be listed in the first row of the table), and the variable ‘event’ identifies an occurrence of the primary endpoint with a 1 and no occurrence of the primary endpoint with a 0. The resulting output in the Column 1 Risk Estimates table in the SAS Output Window provides the individual confidence intervals for each treatment group as well as the confidence interval for the difference between groups.

Additional summaries will be provided to tabulate the total number of vessels transected as well as the specific type of vessel that was transected – pulmonary artery or pulmonary vein. The specific types of interventions that were performed will also be tabulated by randomized treatment group.

The same analysis will be replicated for the primary safety endpoint for the occurrence of hemostatic interventions/procedures completed for post-operative bleeding related to the transection of the PA and PV during VATS lobectomy at the subject level. A similar dataset will be created that contains one record per subject and an indicator for whether or not the subject experienced a post-operative intervention event.

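### The SAP's code lets data order choose the event column, so a SOC arm with no post-operative events would give complemented safety rates, or no risk table if PVS also has none

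*SAP*

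**What the plan says.** SAP 10.4 gives the code for both primary endpoints. The dataset is sorted "by TrtGroup descending event", and the procedure call is "proc freq data=hemo_interv order=data" with the request "tables TrtGroup*event/binomial riskdiff". The accompanying text states that "the SOC group should be listed in the first row of the table" and that the event variable "identifies an occurrence of the primary endpoint with a 1 and no occurrence of the primary endpoint with a 0". It then names the source of the reported figures: "The resulting output in the Column 1 Risk Estimates table in the SAS Output Window provides the individual confidence intervals". The difference between arms is to be read from that table too.

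For safety, the section says: "The same analysis will be replicated for the primary safety endpoint". The safety dataset has one record per subject. SAP 10.7 repeats the safety analysis on the Per Protocol Set. The Table 7 shell asks for a count, a percentage and a 95% interval per arm. It has no row for a difference.

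The only direction the SAP states for a difference is PVS minus SOC (sections 5.1 and 10.4, and Table 6 footnote 2). The SAP does not say what happens when an arm has no events.

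**The concern.** Under `order=data`, the levels of a variable are taken in the order in which they first appear. The descending sort is there so that event=1 appears first and becomes column 1. It does so only if the first-row arm has at least one event. Neither the sort nor the table request fixes the reported level otherwise.

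For the safety endpoint, an arm with no events is a realistic outcome. SAP 5.2 counts only post-operative bleeding that is related to PA/PV transection and leads to transfusion or further surgery. That is much narrower than the intra-operative definition, which also covers compression, clips and energy. At stake are the per-arm rates and intervals of a primary endpoint, which would describe the wrong outcome or be absent if the code were followed literally.

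**Working it through.** **Inputs.** About 200 subjects randomized 1:1, so about 100 per arm (SAP 8). At least 260 firings per group and a 6% intra-operative intervention rate per firing (SAP 8). SOC in row 1, event coded 1/0, Column 1 reported (SAP 10.4). The documents give no safety rate, so a range is assumed, equal in both arms, with subjects independent. The trace below applies the ordering rule that the SAP's own sort step relies on; it was not run in SAS.

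**The plan's own figure.** The per-group margin of error is 1.96 × √(0.06 × 0.94 / 260) = 2.89%, which agrees with the stated maximum of 2.9%. The inputs are therefore read as the SAP intends. The point itself concerns code logic, not this figure.

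**Trace of the code, 100 subjects per arm.** The printed difference is row 1 minus row 2.

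| Events SOC / PVS | Column order | Column 1 risks SOC, PVS | Printed difference | True PVS minus SOC |
|---|---|---|---|---|
| 1 / 2 | 1, 0 | 1%, 2% | -1 point | +1 point |
| 2 / 0 | 1, 0 | 2%, 0% | +2 points | -2 points |
| 0 / 1 | 0, 1 | 100%, 99% | +1 point | +1 point |
| 0 / 2 | 0, 1 | 100%, 98% | +2 points | +2 points |
| 0 / 0 | 0 only | no risk table | none | 0 |

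In the 0 / 2 row the standard error is √(0 + 0.02 × 0.98 / 100) = 0.014, so the printed difference is +2.0 points with limits 2.0 ± 1.96 × 1.4, or -0.7 to +4.7. The same calculation on the event=1 column as PVS minus SOC gives identical values. The difference thus carries the SAP's stated direction here, while both arm-level rates are complements. In the rows where SOC has an event, the rates are right and the printed difference is SOC minus PVS.

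**How likely.** Let q = (1 - p)^100 be the probability that an arm has no events at true rate p. Complemented rates need SOC = 0 and PVS ≥ 1, with probability q(1 - q). No risk table needs both arms at zero, with probability q².

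| Assumed p | q | Complemented rates, q(1 - q) | No risk table, q² |
|---|---|---|---|
| 0.5% | 0.606 | 24% | 37% |
| 1% | 0.366 | 23% | 13% |
| 2% | 0.133 | 12% | 2% |
| 3% | 0.048 | 5% | 0.2% |

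**Performance endpoint.** At 6% and 260 firings, the probability of no SOC event is 0.94^260, about 1 × 10⁻⁷.

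**The case against.** The strongest case on the other side is that the harm is small and hard to miss. Safety has no acceptance criterion: the 3% bound applies to firings only. Table 7 has no difference row. It prints a count beside each percentage, and its footnote 1 fixes the denominator as all subjects in the arm, so a complemented entry would read as zero subjects and 100.0%. That contradicts itself, and also the intervention-type rows below and Listing 16. The procedure by default also prints a Column 2 table, which in this case holds the correct risks. When both arms are at zero, the table is visibly missing and no wrong number can be reported from it. All of this stands, and it is why the point is minor.

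It does not remove the point. The SAP names Column 1 as the source of the per-arm intervals that Table 7 requires. Taking them from elsewhere would depart from the plan after results are seen.

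A reader might infer three stronger things that the documents do not support:

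- **That a SOC arm with no events always inverts the result.** It does not if PVS also has none. The probabilities of a zero SOC arm (61%, 37%, 13% and 5% at the assumed rates) therefore overstate the chance of complemented rates.
- **That the safety difference is reversed, with +2 points printed where -2 is right for 0 against 2 events.** The only direction the SAP states is PVS minus SOC, which is +2. The sign would be wrong only if someone routinely negated the output, a step the SAP does not describe.
- **That the primary performance decision is exposed.** At the plan's own rate it is not.

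**Conclusion.** The point holds as a minor coding fault confined to the primary safety endpoint. Followed literally, SAP 10.4 gives event-free rates and intervals when SOC has no post-operative event and PVS has at least one, and no rates or intervals when neither arm has one. Over assumed rates of 0.5% to 3%, the first case has a probability of about 24% falling to 5%, and the second about 37% falling to 0.2%.

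Separately, the sign of the printed difference is not fixed: it is SOC minus PVS in the ordinary case and numerically equals PVS minus SOC when SOC alone has no events.

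The conclusion rests on about 100 subjects per arm, equal true rates in the two arms, and levels being taken in order of appearance. The probabilities depend on rates the documents do not give; the fault in the code does not.

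**What to change.** In SAP 10.4:

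- Name the event level explicitly. For example, build the four cell counts per endpoint with zero cells retained (`weight count / zeros`), use the internal order 0, 1, request `riskdiff(column=2)` and report the event=1 estimates.
- State that every difference is PVS minus SOC, and derive it so that the sign does not depend on the data.
- State that an arm with no events is reported as 0/n with an exact (Clopper-Pearson) interval, whether or not the procedure prints a risk table. For 0/100 the upper limit is 1 - 0.025^(1/100) = 3.6%.
- Add a programming check that each reported rate equals events divided by records in that arm.

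Swapping the arm order alone is not enough. With PVS in row 1, the same fault arises when PVS has no events and SOC has some.

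Before database lock, run the code in SAS on four dummy datasets: events in both arms, none in SOC only, none in PVS only, and none in either. The cost is a few lines of code and SAP wording, with no new data.

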7.2 DETERMINATION OF SAMPLE SIZE

Approximately 200 subjects will be randomized in the study in a 1:1 ratio to standard of care or powered vascular stapler. Historical clinical study data on a similar powered surgical stapler demonstrated a need for staple line interventions in approximately 6% of firings on the pulmonary artery or pulmonary vein. This data also showed an average of 2.6 to 2.9 firings per subject, and it is expected, given differences in device design, that each subject will require 3 to 4 firings on the pulmonary vein or pulmonary artery in the current study with powered vascular stapler.

Given that it is expected to have a minimum of 260 firings in each group, the sample size of approximately 200 subjects is considered adequate for descriptive summarization of the primary performance endpoint, i.e. number and frequency of intra-operative surgical interventions. Assuming an approximate background intervention rate of 6%, the given sample size will provide reasonable precision in the estimation of the intervention rate to an expected margin of error for a 95% confidence interval of at most 2.9% for each group.

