5.1 Primary Performance Endpoint

The primary performance (effectiveness) endpoint in this study was defined as the occurrence of hemostatic interventions/procedures completed for intra-operative bleeding related to the transection of the PA and PV during VATS lobectomy with the use of either the SOC or PVS stapler. Hemostasis interventions or procedures were defined as bleeding detected and controlled intra-operatively (additional stapling, over-sewing, clip placement, compression, use of suture, sealant, and/or buttress, and/or use of energy); or bleeding that occurred intra-operatively requiring blood or blood product transfusion or an additional surgical procedure (e.g. conversion to open). No hemostasis intervention was defined as no bleeding at the staple line or bleeding that stopped after initial blotting of the staple line.

The primary performance endpoint will be summarized at the firing level as multiple firings per subject were expected and observed; that is, the denominator for the primary endpoint will be the total number of firings and the numerator will be the number of firings where an intervention was required.

During development of the protocol with the Notified Body (TUV) following their decision to grant CE mark to the device, a formal hypothesis was not defined for the study; however, to establish that the intervention rate of PVS is not increased compared to SOC, an acceptance criterion was developed and a 95% confidence interval for the difference in proportion of firings requiring interventions for PVS minus SOC will be calculated. The powered vascular stapler will be considered to have acceptable performance if the upper bound of the 95% confidence interval does not exceed 3%.

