Number of Vessel Transections Requiring Intervention [1] n (%)	xx (xx.x%) xx.x%, xx.x%	xx (xx.x%) xx.x%, xx.x%	xx (xx.x%) xx.x%, xx.x%
95% Confidence Interval for Percent			
Difference (95% CI) for Percent Requiring Transection [2]		xx.x% (xx.x%, xx.x%)	
Type of Intervention, n (%) [3]			
Additional Stapling	xx (xx.x%)	xx (xx.x%)	xx (xx.x%)
Over-sewing	xx (xx.x%)	xx (xx.x%)	xx (xx.x%)
Compression	xx (xx.x%)	xx (xx.x%)	xx (xx.x%)
Use of Suture	xx (xx.x%)	xx (xx.x%)	xx (xx.x%)
Sealant	xx (xx.x%)	xx (xx.x%)	xx (xx.x%)
Buttress	xx (xx.x%)	xx (xx.x%)	xx (xx.x%)
Use of Energy	xx (xx.x%)	xx (xx.x%)	xx (xx.x%)
Clip Placement	xx (xx.x%)	xx (xx.x%)	xx (xx.x%)
Blood Product Transfusion	xx (xx.x%)	xx (xx.x%)	xx (xx.x%)
Additional Surgical Procedure	xx (xx.x%)	xx (xx.x%)	xx (xx.x%)
Other Intervention	xx (xx.x%)	xx (xx.x%)	xx (xx.x%)

[1] Denominator for calculation of percentage is the total number of vessels transected in that group.

[2] Difference is calculated as Powered Vascular Stapler minus Standard of Care Stapler.

[3] Denominator for calculation of percentage is the total number of vessels requiring intervention in that group.

Table 7
Post-Operative Interventions or Procedures Related to Pulmonary Artery or Pulmonary Vein Bleeding
Safety Set

Characteristics	Standard of Care Stapler (N = ##)	Powered Vascular Stapler (N = ##)	Overall (N = ##)
Number of Subjects Requiring Post-Operative Intervention Related to Pulmonary Artery or Pulmonary Vein Bleeding			
n (%) [1]	xx (xx.x%)	xx (xx.x%)	xx (xx.x%)
95% Confidence Interval for Percent	xx.x%, xx.x%	xx.x%, xx.x%	xx.x%, xx.x%
Type of Intervention, n (%) [2]			
Blood Product Transfusion	xx (xx.x%)	xx (xx.x%)	xx (xx.x%)
Additional Surgical Procedure	xx (xx.x%)	xx (xx.x%)	xx (xx.x%)
Other Intervention	xx (xx.x%)	xx (xx.x%)	xx (xx.x%)

[1] Denominator for calculation of percentage is the total number of subjects in that group.

[2] Denominator for calculation of percentage is the total number of subjects requiring intervention in that group.

Table 8
Device Usage Details
Full Analysis Set

Characteristics	Standard of Care Stapler (N = ##)	Powered Vascular Stapler (N = ##)	Overall (N = ##)
Number of Subjects Where Device Was Articulated	xxx	xxx	xxx
Did Articulation Make it Easier to Perform Surgery? [1]			
Yes	xx (xx.x%)	xx (xx.x%)	xx (xx.x%)
No	xx (xx.x%)	xx (xx.x%)	xx (xx.x%)
Was Articulation Essential to Performing the Surgery? [1]			
Yes	xx (xx.x%)	xx (xx.x%)	xx (xx.x%)
No	xx (xx.x%)	xx (xx.x%)	xx (xx.x%)

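### SAP 10.4 judges acceptance on PVS minus SOC, but its code note puts SOC in row 1, so the printed interval runs SOC minus PVS and, used unchanged, could reverse the 3% decision

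*SAP*

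**What the plan says.** The direction of the comparison is the same wherever the documents define it. SAP 10.4 requires that "a 95% confidence interval for the difference in the proportion of firings requiring interventions for PVS minus SOC will be calculated", with acceptance if the upper limit does not exceed 3%. SAP 5.1, Protocol 7.4 and the Protocol synopsis give the same rule. The shell for SAP Table 6 repeats the direction in footnote 2: "Difference is calculated as Powered Vascular Stapler minus Standard of Care Stapler".

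SAP 10.4 then gives the SAS code: a sort by treatment group and descending event, followed by PROC FREQ with `order=data` and a plain `riskdiff` request. The explanation under the code says that "the SOC group should be listed in the first row of the table". It adds that the Column 1 Risk Estimates table "provides the individual confidence intervals for each treatment group as well as the confidence interval for the difference between groups". It gives no instruction to change the sign or exchange the limits.

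**The concern.** With SOC in row 1 and PVS in row 2, the difference printed by PROC FREQ is SOC minus PVS, the opposite of the quantity that the acceptance rule needs. The SAP nevertheless presents that output as the interval to use.

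The rule looks at one limit only, so the direction decides the result. The upper limit of PVS minus SOC guards against PVS causing more interventions. The upper limit of SOC minus PVS guards against SOC causing more. Read the wrong way round, the rule could accept a stapler that needs more hemostatic interventions than SOC and refuse one that needs fewer.

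This is the study's only acceptance criterion. SAP 5.1 and section 6 specify no hypothesis and no p-value, so no parallel test would reveal a reversed direction.

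**Working it through.** **Inputs**

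- Firings: at least 260 per group (Protocol 7.2, SAP 8), that is 100 subjects × 2.6 firings.
- Rate: "Assuming an approximate background intervention rate of 6% in each group" (SAP 8).
- Acceptance limit: 3% (SAP 10.4).
- Interval: Wald, taken as the `riskdiff` default.
- Subtraction: row 1 minus row 2. This is standard SAS behaviour, not stated in the documents and not run here.
- PVS rates other than 6%, and all intraclass correlations, are illustrative assumptions.

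**The plan's own figure.** The half-width for one group is 1.96 × √(0.06 × 0.94 / 260) = 2.887%. This reproduces the stated margin of at most 2.9%.

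**What fixes the direction.** The sort puts event = 1 first, so column 1 is the intervention column provided that row 1 contains at least one event. At 6%, the chance that SOC has none is 0.94^260, about 1 in 10 million. The code lines alone do not fix the row order, because the coding of the treatment variable is not given. The row-order note does fix it: row 1 is SOC.

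**One data set, both directions.** Take SOC 16/260 (6.15%) and PVS 20/260 (7.69%).

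- Standard error = √(0.0615 × 0.9385/260 + 0.0769 × 0.9231/260) = 2.225%.
- PVS minus SOC: +1.54% ± 1.96 × 2.225%, giving −2.8% to +5.9%. The upper limit exceeds 3%, so the criterion is not met.
- SOC minus PVS, as printed: −1.54%, giving −5.9% to +2.8%. Read unchanged, this is below 3% and would pass.

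**Flip points with SOC at 16/260**

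| PVS events out of 260 | Intended direction | Printed direction |
|---|---|---|
| 13 or fewer | pass (upper limit 2.79% at 13) | fail (5.10% at 13) |
| 14 to 19 | fail | fail |
| 20 or more | fail (5.90% at 20) | pass (2.82% at 20) |

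**Probability of being called acceptable.** For each pair of event counts, the two binomial probabilities were multiplied, then summed over the pairs whose upper limit is at most 3%. Firings are treated as independent, 260 per arm, SOC 6%.

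| True PVS rate | Intended | Printed, used unchanged |
|---|---|---|
| 3% | 92.5% | 3.3% |
| 6% | 31.2% | 31.2% |
| 7.5% | 10.6% | 53.9% |
| 9% | 2.7% | 74.3% |

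At 6% in both arms the totals agree but the individual trials do not: the two directions give opposite decisions in 62.3% of trials, and both fail in the other 37.7%.

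**Sensitivity**

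- Lower equal rates: at 2% in both arms, 39.3% of trials pass both ways and 60.4% differ. At 1%, 81.5% pass both ways and 18.5% differ.
- More PVS firings: Protocol 7.2 expects that "each subject will require 3 to 4 firings on the pulmonary vein or pulmonary artery in the current study with powered vascular stapler". With 300 or 400 PVS firings against 260 for SOC, and PVS at 9%, the chances are 2.6% versus 78.1% and 2.2% versus 83.5%.
- Correlated firings: beta-binomial simulation, 100,000 trials, 100 subjects per arm (60 with 3 firings, 40 with 2), PVS at 9%. The chances are about 3% versus 73% at an intraclass correlation of 0.05, and about 5% versus 72% at 0.2.

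**The case against.** The case for leaving this alone is that the plan is clear about what it wants. The direction is stated in four places in the text and again in Table 6, whose footnote governs the number reported. Every two-arm table shell lists SOC first, so the row-order note may only have been meant to match that layout, with the sign change left as routine programming. Labels such as PVS and SOC would also sort PVS first and give the right direction. A slip would be visible: in the example above, 6.2% for SOC and 7.7% for PVS would sit above a difference of −1.5% labelled PVS minus SOC. Finally, the subtraction order comes from knowledge of SAS and not from the documents, and nothing shows how likely it is that the printed limit would be used unchanged.

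Most of this stands, and it lowers the likelihood of harm. It does not remove the contradiction. The Table 6 footnote is a label, not a computing step, and it conflicts with the code note. An alphabetical sort that puts PVS first would break the SAP's explicit instruction. SAP 10.4 also carries the same analysis over to the primary safety endpoint, where the Table 7 shell has neither a row for the difference nor a footnote on direction.

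**Conclusion.** The concern holds. Within SAP 10.4, the row-order note conflicts with the direction of the acceptance rule, and no text tells the programmer to reverse the interval. The conclusion rests on PROC FREQ subtracting row 2 from row 1.

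The sizes are conditional on the printed upper limit being compared with 3% unchanged. They describe the consequence of that slip, not the operating characteristics of the intended rule. On that condition the effect is large at the planning rate and small only when both rates are very low. The estimand, the 3% limit and the decision rule are not affected. The point should be fixed because it concerns the decisive analysis and costs almost nothing to repair.

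**What to change.** In the code note of SAP 10.4, require PVS in the first row, for example with the treatment variable coded 1 = PVS and 2 = SOC, so that row 1 minus row 2 is PVS minus SOC.

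Alternatively, keep SOC first and state that the printed estimate and limits are negated and the limits swapped before entry in Table 6 and comparison with 3%. This is equivalent to requiring that the lower limit of SOC minus PVS be at least −3%.

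Either change costs one phrase or sentence. The acceptance rule, the data and Table 6 stay as they are.
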